reflex^{21,22}, increases corticospinal excitability²⁴, and increases motor unit recruitment.⁴¹ We propose to deliver tsDCS using an electrode montage that targets lumbar spinal excitability, and has been validated by modeling of electrical current flow⁴² and by gains in lower extremity motor performance.²⁵ The objective with tsDCS is to bring spinal neurons closer to their discharge threshold. When applied during walking, this increased excitability of spinal neurons contributes to a physiological environment that is more responsive to task-specific activation by descending/motor and afferent/sensory pathways.²² The proposed study is designed to provide evidence of short term effects of tsDCS on task practice, which can be translated to longer rehabilitation interventions in the future.

5. Specific Aims:

Specific Aim 1: Acquire preliminary data to assess whether active tsDCS and/or textured shoe insoles improve practice-related gains in performance and retention for a complex obstacle walking task.

Hypothesis 1a: Within-session, effect sizes will support the following group differences for improved walking speed and reduced prefrontal activity after the practice period:
[active/textured] > [active/smooth = sham/textured] > [sham/smooth]

Hypothesis 1b: At the 2-day retention test, effect sizes will support the same findings described for Hyp 1a.

Specific Aim 2: Establish evidence of increased spinal excitability following tsDCS.

Hypothesis 2: Spinal excitability post-stimulation (measured by H-reflex) will be significantly elevated above pre-stimulation baseline for active tsDCS but not sham tsDCS.

6. Research Plan:

Study Overview

All study procedures will be conducted at the Brain Rehabilitation Research Center within the Malcom Randall VA Medical Center. Up to forty older men and women will be enrolled in the intervention component of this study. A larger number will be enrolled for onsite screening, because some will fail the screening tests and not proceed to the study intervention.

Participants will undergo the following sequence of events:

- *Telephone Screening:* Volunteers will be screened by telephone to determine if they meet basic enrollment criteria including age and general health status.

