- Cognitive Assessment Battery from Cambridge Brain Sciences, which includes up to 12 cognitive tests. All are short, simple, computer-based assessment that assess domains of cognitive such as spatial working memory, response inhibition, and reasoning. A specific example is the visuospatial working memory test, in which participants are asked to remember the sequence and location of shapes that appear and disappear from the screen.

Following the screening visit, study staff will evaluate performance/responses relative to the study enrollment inclusion/exclusion criteria. Medical records may be examined to verify absence of exclusion diagnoses, and to obtain complete/accurate medication lists. Individuals who meet all criteria will be invited to enroll in the full study.

At the discretion of the Principal Investigator, any individual may be deemed ineligible for further participation in this study if there are concerns about the individual's capability to perform study procedures or if it may be unsafe for the volunteer to participate in the study. Furthermore, minor exceptions to the inclusion/exclusion criteria may be permitted at the discretion of the Principal Investigator if those exceptions do not influence participant safety. For example, small deviations from the target range of walking speed or somatosensory function. This is important to ensure that individuals are not excluded for insignificant reasons and to facilitate meeting enrollment benchmarks.

Walking Practice Visit(s)

Walking practice protocol

Walking practice will consist of 10-20 passes over a 10-meter complex walking course consisting of foam obstacles of various heights and widths, as well as transitioning between hard (bare floor) and soft surfaces (exercise mats). Each pass will be separated by a short rest period of approximately one minute. Participants will be instructed to walk as fast as safely possible.

For most participants, the walking practice protocol will be completed in a single visit. However, a subset of participants (up to 20) will perform the walking practice protocol twice so that we can study dosage effects (i.e., one session versus two sessions). This subset will be selected randomly.

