During the walking practice protocol, participants will receive either active or sham transcutaneous spinal direct current stimulation (tsDCS) and will wear either smooth or textures shoes insoles. Specifically, participants will be randomized to one of four groups: active tsDCS with smooth insoles (*active/smooth group*); 2) sham tsDCS with smooth insoles (*sham/smooth group*); 3) active tsDCS with textured insoles (*active/textured group*); and 4) sham tsDCS with textured insole (*sham/textured group*). More detail about tsDCS and insoles are given below.

Transcutaneous spinal direct current stimulation (tsDCS) during walking practice protocol
tsDCS will be delivered to the posterior lumbar region of the spinal cord during walking using a commercially available direct current stimulation unit (Soterix Medical Inc). Each tsDCS electrode is comprised of a carbon rubber electrode encased in a saline-soaked sponge. The anode electrode will be placed on the skin over the 11th and 12th thoracic vertebrae, and the cathode electrode will be placed over the umbilicus. This electrode configuration has been shown to appropriately target the lumbosacral spinal cord, as validated by modeling of electrical current flow⁴² and by gains in lower extremity motor performance.²⁵ A standard dosage of up to 30 continuous minutes of 2.5 mA stimulus will be used. This dosage (or similar) has been used in numerous prior studies and has been shown to be well-tolerated and to produce measurable changes in reflex activity and/or lower extremity motor performance.^{23-25,38,39,43,44} An identical electrode arrangement will be used for the sham condition, except the stimulation will be delivered in a brief ramp-like manner for just a few seconds at the beginning and end of the stimulation period. This sham approach is widely used in the field of direct current stimulation, and has been reported to be indistinguishable from active stimulation.^{39,45} This is because participants quickly habituate to the sensation of active stimulation.

Textured Shoe Insoles during walking practice protocol

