Prefrontal brain activity may be measured with fNIRS during walking and cognitive assessments. fNIRS is a safe non-invasive technology for indirectly assessing cortical activation based on changes in blood flow and oxygenation. Sensors are placed on the forehead, and produce infrared light that is able to pass through the skull and is absorbed or reflected by blood and other tissues in the head. Infrared light is considered safe and there is no sensation association with this procedure. Calculations made from the relative amount of light absorption/reflection provide an estimate of the metabolic activity level of underlying cortical tissue. We will use a commercially available fNIRS monitor (Octamon by Artinis Medical Systems).

Muscle activity with surface electromyography (EMG)

EMG is a non-invasive approach to measuring the timing and amplitude of neuromuscular activity by placing recording sensors over the muscles. We may record EMG during walking assessments from up to 8 muscles per leg. Adhesives will be used to secure the electrodes to the legs. Prior to electrode placement, the recording site will be shaved and cleaned to ensure good quality contact.

H-reflex of the soleus muscle to assess spinal excitability

H-reflex testing involves delivering an electrical stimulus to the peripheral nerve and measuring the resultant muscle activity using surface electromyography. H-reflex assessment of the soleus muscle may be conducted immediately preceding tsDCS, as well as immediately post-tsDCS and at 30 minutes post-tsDCS. H-reflex may also be recorded while the participant rests in a semi-reclined positioned with the foot supported in slight ankle dorsiflexion (10 degrees) and the knee in 30 degrees of flexion. H-reflex may also be recorded while the participant is walking on a treadmill or overground. Stimulation will be delivered via a cathode placed in the popliteal fossa and an anode placed above the patella. Electromyography (EMG) will be recorded from the soleus with bipolar surface electrodes place 3 cm apart. Electrode placement will be along the mid-dorsal line of the leg, 4cm below where the gastrocnemius joins the Achilles tendon.

Sympathetic nervous system activity measured by skin conductance

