
fNIRS Safety: fNIRS poses no safety risk. Infrared light from the fNIRS device is not harmful and elicits no sensation. Sensors may be secured to the skin using adhesive tape, which could lead to mild skin irritation in those who are sensitive to adhesives. If a person indicates or displays such a sensitivity, we will avoid using adhesive tape and instead use elastic fabric or straps to secure the sensors.

Questionnaire administration: Questionnaire data are collected in secure spaces where the interview cannot be overheard. Participants will be informed that they are not required to answer questions that they do not wish to answer.

Statistical Analysis Plan: Effect sizes for between-group differences will be calculated for *improved* walking speed after the practice period. For Hypothesis 1b, an analogous comparison

will be made for the 2-day retention test. We do not claim that this study is powered to conduct statistically significant tests of group differences, although we will examine our data for evidence of directional effects:

[active/textured] > [active/smooth = sham/textured] > [sham/smooth].

Rather, our goal is to calculate effect sizes and variance of response in order to provide data needed for powering a future full scale trial. This study will also provide information on the feasibility of our protocol including safety and recruitment.

1. Fielding, R.A., W.J. Rejeski, S. Blair, T. Church, M.A. Espeland, T.M. Gill, J.M. Guralnik, F.C. Hsu, J. Katula, A.C. King, S.B. Kritchevsky, M.M. McDermott, M.E. Miller, S. Nayfield, A.B. Newman, J.D. Williamson, D. Bonds, S. Romashkan, E. Hadley, M. Pahor, and L.R. Group, *The Lifestyle Interventions and Independence for Elders Study: design and methods*. Journals of Gerontology. Series A, Biological Sciences and Medical Sciences, 2011. **66**(11): p. 1226-37.
2. Shumway-Cook, A., A. Patla, A. Stewart, L. Ferrucci, M.A. Ciol, and J.M. Guralnik, *Environmental components of mobility disability in community-living older persons*. J Am Geriatr Soc, 2003. **51**(3): p. 393-8.
3. Shumway-Cook, A., A.E. Patla, A. Stewart, L. Ferrucci, M.A. Ciol, and J.M. Guralnik, *Environmental demands associated with community mobility in older adults with and without mobility disabilities*. Phys Ther, 2002. **82**(7): p. 670-81.

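### Hypothesis 2 judges each arm against its own baseline, and the SAP has no active-versus-sham H-reflex comparison

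*Combined protocol and SAP*

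**What the plan says.** Specific Aim 2 is to "Establish evidence of increased spinal excitability following tsDCS". Its one hypothesis is that spinal excitability after stimulation, measured by H-reflex, "will be significantly elevated above pre-stimulation baseline for active tsDCS but not sham tsDCS". No test, model or alpha is named.

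The Statistical Analysis Plan covers walking speed: "Effect sizes for between-group differences will be calculated for" improved walking speed after practice, with an analogous comparison at the 2-day retention test. It makes no claim of power for significance tests of group differences, and states that "our goal is to calculate effect sizes and variance of response in order to provide data needed for powering a future full scale trial". It does not mention H-reflex.

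On conduct, the Walking Practice Visit(s) section says: "During the walking practice protocol, participants will receive either active or sham transcutaneous spinal direct current stimulation". The practice itself is described thus: "Walking practice will consist of 10-20 passes over a 10-meter complex walking course". The H-reflex section says: "H-reflex assessment of the soleus muscle may be conducted immediately preceding tsDCS, as well as immediately post-tsDCS and at 30 minutes post-tsDCS". It allows recording while semi-reclined, on a treadmill or overground. Some participants have two sessions: "a subset of participants (up to 20) will perform the walking practice protocol twice so that we can study dosage effects".

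**The concern.** Aim 2 is the study's mechanistic claim: that tsDCS raises spinal excitability. Supporting it requires showing that active stimulation does something sham does not. The stated criterion instead asks whether each arm moved significantly from its own baseline. One arm can cross the significance line and the other fall just short while the two differ by very little.

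The design makes this more than a formal point. Active and sham are both given during obstacle walking, so practice, fatigue and elapsed time lie between the pre and post measurements in both arms. Sham control exists to subtract such a shared change, and the criterion does not subtract it. Two errors follow:

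- With a shared rise and no tsDCS effect, active may reach significance and sham miss it by chance, and Aim 2 is reported as supported.
- With a real tsDCS effect, a shared rise can also make sham significant, or a shared fall can hide the active rise. Aim 2 is then reported as not supported.

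The plan also commits to no between-arm H-reflex effect size, although effect sizes for a later trial are the SAP's stated purpose.

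**Working it through.** The documents give no H-reflex power, alpha, SD or effect size, so there is no planned figure to reproduce. The check is of how the criterion behaves if applied as worded.

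**Inputs**

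- From the documents: up to 40 participants, four groups, two of them active and two sham.
- Assumed: equal allocation, all evaluable, so n = 20 per stimulation arm pooled over insoles; paired t-tests at two-sided 0.05, with a rise required; changes in units of the SD of the pre-post change; shared change and tsDCS effect varied over a range.

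**Formulas**

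For an arm with true mean change d, let p(d, n) be the probability that a paired t-test is significant upward. This is the upper tail of a noncentral t with n − 1 degrees of freedom and noncentrality d√n, beyond the critical value (2.093 for n = 20).

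P(Hypothesis 2 supported) = p(d_active, n_active) × [1 − p(d_sham, n_sham)].

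The comparator is a two-sample t-test on change scores with 38 degrees of freedom and critical value 2.024.

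**1. No true tsDCS effect (d the same in both arms, n = 20 each)**

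| Shared change (SD) | p per arm | p × (1 − p) |
|---|---|---|
| −0.3 | 0.0006 | 0.06% |
| −0.2 | 0.0025 | 0.25% |
| 0 | 0.025 | 2.4% |
| +0.2 | 0.134 | 12% |
| +0.3 | 0.247 | 19% |
| +0.46 | 0.497 | 25% |
| +0.6 | 0.721 | 20% |
| +0.8 | 0.924 | 7% |

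With equal arms p(1 − p) cannot exceed 0.25, and reaches it where p = 0.5. A direct test finds active higher 2.5% of the time in every row. In simulation at a shared rise of 0.5 SD, about 90% of the results that met the criterion showed no significant between-arm difference.

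The ceiling moves if evaluable numbers differ: 30% with 20 active and 16 sham, 20% with 16 active and 20 sham.

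**2. True tsDCS effect of 0.9 SD (n = 20 each)**

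| Shared change (SD) | P(active up) | P(sham up) | Criterion met | Direct test |
|---|---|---|---|---|
| −0.4 | 0.564 | 0.000 | 56% | 79% |
| −0.2 | 0.844 | 0.003 | 84% | 79% |
| 0 | 0.968 | 0.025 | 94% | 79% |
| +0.2 | 0.997 | 0.134 | 86% | 79% |
| +0.46 | 1.000 | 0.497 | 50% | 79% |
| +0.7 | 1.000 | 0.844 | 16% | 79% |

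For the direct test the noncentrality is 0.9 × √(20/2) = 2.85, whatever the shared change, because that change cancels.

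**3. Precision of the direct comparison**

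The unadjusted 95% confidence interval has half-width 2.024 × √(2/20) = 0.64 SD. Power of 80% needs a difference of about 0.91 SD.

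**The case against.** The strongest reply is that Hypothesis 2 describes an expected pattern and is not a decision rule. No test is named, so the probabilities above belong to an assumed procedure. That is fair as to the exact figures. But the sentence speaks of significance against each arm's own baseline, and neither the SAP nor any other section offers another way to decide Aim 2.

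The second reply is that harm requires a shared change, which the documents neither assert nor quantify. This stands. With none, false support is 2.4%, no worse than the direct test; a shared fall makes it rarer still; and 25% is a mathematical ceiling for equal arms, not a forecast. The criterion also has the higher success rate at a true 0.9 SD for shared changes from about −0.24 to +0.26 SD. Part of that advantage is bought with false support, which is already 12% at +0.2 SD. A randomised sham comparison should not have to rest on an unverified absence of drift.

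Third, a between-arm effect size could be worked out from the two within-arm means and SDs. True, so the gap is one of commitment: nothing prevents the calculation and nothing plans it.

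Last, this is a pilot that disclaims power for group tests. That limits the severity. It does not defend the wording, since Hypothesis 2 itself invokes significance, and a between-arm estimate suits a pilot better than two verdicts.

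**Conclusion.** The concern holds. That the criterion is two within-arm verdicts, and that the SAP contains no active-versus-sham H-reflex comparison, is clear from the text and needs no assumption. The size of the consequence does: it depends on a shared pre-post change of unknown size and direction, and on the assumed 20 per arm, paired t-tests and two-sided 0.05. Over the range examined, false support runs from under 0.1% to 25% (30% with 20 active and 16 sham evaluable), and success at a true 0.9 SD effect runs from 94% down to 16%. The direct comparison holds at 2.5% and 79%.

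This should be fixed, but it does not threaten the study. It bears on the mechanistic aim alone.

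**What to change.** Restate Hypothesis 2, and add a matching paragraph to the SAP, as the active-minus-sham difference in post-stimulation H-reflex, pooled over insole type and adjusted for the pre-stimulation value and insole factor, reported as an estimate with a 95% confidence interval. Drop the requirement that sham not be significant. Within-arm changes can still be shown descriptively.

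As a secondary point, name one post-stimulation time, one recording condition and one session as the main comparison, for example immediately post-tsDCS, semi-reclined, first practice session, and label the rest secondary. The H-reflex section lists the times and conditions only as things that may be done, so the chosen measurement should be made a firm part of the visit.

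The cost is one paragraph of wording. No extra participants are needed, and no measurements beyond the pre and post H-reflex that Hypothesis 2 already requires. The statistical cost is lower power if there is truly no shared change (79% against 94% at 0.9 SD), and an interval of about ±0.64 SD. Both figures are for unadjusted change scores; the gain from baseline adjustment cannot be computed without a pre-post correlation, which the documents do not give. The result will therefore serve mainly as an estimate, which is what the SAP says the study is for.

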Coversheet

Protocol

Spinal excitation to enhance mobility in elderly adults

NCT03667573

06/23/2021

Protocol

1. Project Title

Spinal Excitation to Enhance Mobility in Elderly Adults: "The Charge Study"

2. Investigator(s):

[name]

[name] PT

3. Abstract:

It is well known that age-related impairments of the brain and peripheral nerves contribute to a decline in walking function. Age-related impairment of the spinal cord is also a likely contributing factor, as the literature describes a variety of changes in spinal cord structure and function with aging. Specifically, the elderly spinal cord is less excitable, conducts signals more slowly, and is subject to neural noise. Therefore, we are initiating a new line of research with the goal of enhancing walking function in older adults by intervening on age-related neural impairment of the spinal cord. The objective of the proposed study is to establish the feasibility, preliminary efficacy, and variance of response for using transcutaneous spinal direct current stimulation (tsDCS) and textured shoe insoles to excite spinal locomotor circuits and enhance practice-related performance and retention on an obstacle walking task. Enhanced practice and retention effects will support future efforts to translate this approach into a longer term rehabilitation intervention.

Excitatory tsDCS is a non-invasive neuromodulation approach in which a relatively weak electrical current is delivered to the desired region of the spinal cord via electrodes placed on the skin. The electrical current does not cause discharge of action potentials, but rather is designed to bring neurons closer to their discharge threshold by inducing a sub-threshold depolarization of membrane potentials. When combined with a behavioral task, tsDCS has the potential to upregulate neural circuits in a task-specific manner and promote Hebbian neuroplasticity ('fire together, wire together'). We will use a previously established electrode montage to deliver excitatory tsDCS to the lumbosacral spinal cord during practice of a complex obstacle walking task.

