We also propose to combine the use of textured shoe insoles with tsDCS. This combinatorial approach may be a potent strategy for simultaneously optimizing spinal responsiveness to input from both descending and ascending excitatory signals to spinal centers of locomotor control. One anticipated benefit of increasing the excitation of spinal locomotor circuits is a reduction in the executive demand of walking, as measured by prefrontal cortical activation. Our research shows that elderly adults rely heavily on compensatory executive control while walking. This is widely considered to be a risk factor for adverse outcomes including falls.

We propose a parallel groups study design in which 40 older adults who have walking deficits and who demonstrate a compensatory executive locomotor control strategy will be randomized into one of four groups: 1) active tsDCS with smooth insoles (active/smooth); 2) sham tsDCS with smooth insoles (sham/smooth); 3) active tsDCS with textured insoles (active/textured); and 4) sham tsDCS with textured insole (sham/textured). Participants will be blinded to group assignment. While receiving stimulation for up to 30 minutes, participants will engage in walking practice over a standardized obstacle course. Practice-related gains in performance will be quantified by walking speed and other biomechanical metrics. Retention of performance gains will also be assessed at a separate visit 2 days later. tsDCS-induced changes in spinal excitability will be assessed by measuring soleus H-reflex. Executive demand of walking will be assessed as prefrontal cortical activation, measured with functional near infrared spectroscopy (fNIRS). Intervening on age-related impairment of the spinal cord to improve walking function is

a promising but untapped area of research. The proposed intervention techniques are low cost and translatable to real-world settings, which enhances the potential long term impact of this work on the well-being of older adults.

4. Background:

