People with walking deficits have higher rates of morbidity and mortality, more hospitalizations, poorer quality of life, and are less likely to remain independent in the community.¹⁻¹⁰ Preserving walking function has become a major public health priority as it would drastically reduce health care costs and improve quality of life for many older Americans and their families.¹¹ Data from the American Community Survey (Profile of Veterans: 2011) shows that over 65% of Veterans are age 55 or older. The median age of male Veterans is 64. Therefore, a very large proportion of the Veteran population is currently or will soon be at risk for the well-known decline of walking function that occurs with aging. Preserving walking function is therefore crucial to the personal well-being of aging Veterans and has considerable fiscal and pragmatic implications for the VA Health Care System.

The spinal cord has a critical role in the control of walking. The lumbar spinal cord contains complex circuits called central pattern generators (CPGs) that contribute to patterned muscle activation needed for intra- and inter-limb coordination of walking.^{12,13} During complex walking tasks such as obstacle crossing, the spinal cord must transmit descending motor commands from the brain that are needed to adapt the stepping pattern in order to meet environmental demands or task objectives (e.g., clearing the obstacle). These descending signals are integrated with ongoing activity of the CPGs, and this process is critical to successful stepping adaptations.¹⁴ The spinal cord is also crucial for receiving and transmitting somatosensory information from the periphery, which is an important source of excitation to CPGs¹⁵⁻¹⁷ and also important for eliciting reflex responses to unexpected perturbations (e.g., striking an obstacle).^{18,19} Somatosensory information is also a crucial source of feedback for motor learning.^{20,21} In the proposed project we seek to upregulate these spinal control mechanisms using tsDCS²²⁻²⁵ in order to enhance performance and retention of walking on a complex obstacle course. The obstacle course task was selected because it engages all of the aforementioned roles that the spinal cord serves during walking.

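### Hypothesis 2 judges tsDCS by two separate within-arm H-reflex results and ignores insole; if insoles affect the H-reflex this can mislead in either direction, whereas an active-minus-sham contrast would not

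*Combined protocol and SAP*

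**What the plan says.** Aim 2 (Section 5, Specific Aims) is to "Establish evidence of increased spinal excitability following tsDCS". Its hypothesis is that the post-stimulation H-reflex "will be significantly elevated above pre-stimulation baseline for active tsDCS but not sham tsDCS". These are two within-arm comparisons with baseline. Insole does not appear in either.

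The design crosses current with insole, giving active/smooth, sham/smooth, active/textured and sham/textured. Textured insoles are therefore worn in one of the two sham arms and one of the two active arms. On size: "Up to forty older men and women will be enrolled in the intervention component of this study".

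The protocol gives the insoles a spinal role. The Abstract states the objective as using "transcutaneous spinal direct current stimulation (tsDCS) and textured shoe insoles to excite spinal locomotor circuits", and describes the combination as "simultaneously optimizing spinal responsiveness to input from both descending and ascending excitatory signals to spinal centers of locomotor control". The Background calls "somatosensory information from the periphery, which is an important source of excitation to CPGs".

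Insoles are worn during practice, together with the active or sham current. The H-reflex subsection of the Research Plan says recordings may be made just before tsDCS, straight after it and 30 minutes later, and at rest, on a treadmill or overground. It does not say which insole, if any, is worn at each recording.

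The Statistical Analysis Plan paragraph covers effect sizes for walking speed. It contains no H-reflex analysis, disclaims power for group tests, and gives its purpose as estimating effect sizes and variance for a later trial.

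**The concern.** Hypothesis 2 reads as a decision pattern: significant in active, not significant in sham. It supports a conclusion about tsDCS only if nothing else moves the H-reflex between the pre and post recordings. By the protocol's own rationale something else might, because half of the arms on each side practise in insoles meant to add excitatory input.

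If that input leaves a trace in the post-practice H-reflex, two errors become possible. Sham may rise because of sham/textured, and the pattern then fails although the current works. Active may rise because of active/textured while sham happens to miss significance, and the pattern is then met although the current does nothing. Aim 2 is the study's mechanism check, so either error would pass a wrong signal to the future trial that this study is meant to inform.

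**Working it through.** The documents give no alpha, H-reflex effect size, SD or power for Hypothesis 2, so there is no stated figure to reproduce. What follows is an illustration.

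**Inputs**
- From the documents: up to 40 participants, four arms, two of them textured (one sham, one active).
- Assumed: equal allocation (40/4 = 10 per arm); within-arm SD of pre-to-post change = 1; additive insole effect e and tsDCS effect δ, both in SD units; no effect of sham current or of practice; two-sided 5% tests with only upward rejections counted; the two arms on each side pooled, which is the plain reading of Hypothesis 2 but is not specified.

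**Within-arm test on sham (n = 20)**
- Mean change = (10·0 + 10·e)/20 = e/2. SD = √(1 + e²/4).
- At e = 0.5: 0.25/1.031 × √20 ≈ 1.08. At e = 0.8: 0.40/1.077 × √20 ≈ 1.66. The critical t on 19 df is 2.09.
- By simulation, a significant rise occurs in 17% and 34% of trials, against 2.5% at e = 0.

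**Full pattern (active significant, sham not)**
The two sides are independent, so the rate is P(active rises) × [1 − P(sham rises)]. Two examples:
- δ = 0, e = 0.5: 0.17 × 0.83 = 0.14.
- δ = 0.8, e = 0.8: 0.998 × 0.662 = 0.66.

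Simulation (200,000 trials per setting) gives:

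| e | Sham rises | Pattern met, δ = 0 | Pattern met, δ = 0.5 | Pattern met, δ = 0.8 |
|---|---|---|---|---|
| 0 | 2.5% | 2.4% | 55% | 90% |
| 0.3 | 9% | 8% | 71% | 89% |
| 0.5 | 17% | 14% | 73% | 82% |
| 0.8 | 34% | 22% | 63% | 66% |

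Down each of the last three columns the effect of the current is fixed, yet the rate moves with the insole effect. It rises at δ = 0, rises and then falls at δ = 0.5, and falls at δ = 0.8.

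**Between-arm contrast with insole as a factor**
- Active mean = δ + e/2; sham mean = e/2; the difference is δ for any e. With insole in the model this does not need equal allocation.
- At δ = 0 the contrast is significant upward in 2.5% of trials for every e from 0 to 1.0.
- At δ = 0.5 and 0.8 the mean estimate is 0.50 and 0.80, with power of about 34% and 69%. The within-arm test on active alone, with no insole effect, has about 56% and 92%.
- 95% interval half-width (36 df, t = 2.03): 2.03 × √(1/20 + 1/20) ≈ 0.64 SD overall, and 2.03 × √(1/10 + 1/10) ≈ 0.91 SD within one insole type.

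**Sham/smooth alone (n = 10)**
The chance of a significant rise stays near 2.5% whatever e is.

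**The case against.** The strongest objection is that no insole effect on the post-practice H-reflex is documented. The protocol claims lasting changes in excitability for tsDCS, not for insoles, and Aim 2 is about tsDCS. Insoles could help while worn and leave no trace in a resting recording. If the same insoles were worn before and after, their immediate effect would cancel and only carry-over would remain. This stands, and it makes the size of the problem unknown, possibly nil. It does not remove the point, because recording posture and insole condition are left open.

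The direction is not fixed either. At a tsDCS effect of 0.5 SD, the insole effects tabulated make the pattern easier to meet, and serious failure at 0.8 SD needs a large insole effect. This also stands, which is why the claim is that the pattern can mislead both ways.

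Three stronger readings are tempting, and the documents do not support them:
- *That Hypotheses 1 and 2 contradict each other over sham/textured.* Hypothesis 1 ranks the arms on walking speed and prefrontal activity, and Hypothesis 2 concerns the H-reflex. The Abstract links reduced executive demand to spinal excitation, so there is some tension, but different predictions for different outcomes are not a contradiction.
- *That the study cannot tell which treatment moved excitability.* The crossed layout can, through active minus sham. The weakness lies in the wording of the hypothesis.
- *That the planned analysis inflates the error variance by pooling over insole.* No H-reflex analysis is specified, pooled or otherwise.

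**Conclusion.** The point holds as a weakness in how Hypothesis 2 is framed. Two within-arm significance results are a poor test of tsDCS when half of the arms on each side also receive an intervention described as spinally excitatory. The 2x2 design is sound and already contains what is needed.

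The size is conditional. With 10 per arm, SD 1 and an additive insole effect of 0.5 to 0.8 SD that reaches the post-practice H-reflex, the pattern would be met in 14% to 22% of trials with inert current, and missed in 18% to 34% of trials with a tsDCS effect of 0.8 SD (10% with no insole effect). At an insole effect of 0.3 SD or less the distortion is small for a strong tsDCS effect. With no carry-over it disappears. None of these effect sizes comes from the documents. The case for changing the wording rests mainly on the change being almost free.

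**What to change.** - Restate Hypothesis 2 as the active-minus-sham difference in pre-to-post H-reflex change, naming which post-stimulation recording is used. Estimate it with insole as a factor and report it with a 95% confidence interval.
- Show the active-minus-sham difference within smooth and within textured insoles descriptively, at about 10 per arm. Sham/textured minus sham/smooth can be shown in the same way.
- Limit the statement that no rise is expected to sham/smooth.
- Add this analysis to the Statistical Analysis Plan paragraph, and state the insole condition at each H-reflex recording so that the reader knows whether an immediate insole effect could enter the change.
- Reconcile the opening sentence of the textured-insole subsection in the Research Plan, which has every participant tested with both insole types, with the four parallel groups. Read literally, it would expose all sham participants to textured insoles.

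The cost is a reworded hypothesis, a short addition to the analysis plan and one procedural statement. No new data or participants are needed. The downside is that the between-arm contrast reaches significance less often than the within-arm test (about 34% at 0.5 SD and 69% at 0.8 SD under the assumptions above). It should therefore be presented as an estimate with an interval, in keeping with the plan's stated purpose.
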